17. GENERAL OBLIGATIONS, AGREEMENTS AND ORGANISATION

17.1 Data Protection and Confidentiality

Data protection will be carried out in accordance with the Principles of the General Data Protection Regulation. This will apply to all study data in whatever format it is collected and recorded.

17.2 CRFs and Handling

Electronic CRFs will be used in this trial. Should any corrections or amendments be necessary, data clarification requests will be forwarded to the Investigator or designee.

17.3 Quality Control and Monitoring

The conduct of the study will be monitored by appropriately qualified staff from the Sponsor and/or an organisation authorised to conduct activities on the Sponsor's behalf. Risk based monitoring will be used. For further specifications please refer to the monitoring plan. The Sponsor will retain the responsibility for monitoring and may delegate this responsibility via a contract and/or Monitoring Manual.

The study will be monitored at regular intervals and the frequency of monitoring visits will be determined by the rate of subject recruitment. The following will be reviewed at these visits:

- Responsibilities of the Investigator and the study site under GCP requirements
- Compliance with the protocol
- Consent procedure
- Source Data Verification (SDV)
- Procedures for AEs
- Storage and accountability of study vaccine

The purpose of SDV is to verify, so far as is possible, that the information in the CRF reflects the data recorded in the subject's source data records. SDV will be performed with due regard for subject confidentiality. SDV will be undertaken on an ongoing basis as part of the monitoring visits. Direct access to the source documents will be required. The monitor will make a direct comparison with data entered in the subject CRFs and the source data.

The Investigator must permit the monitor, the Sponsor's internal auditors and representatives from the Regulatory Authorities to inspect all study-related documents and pertinent source data records for confirmation of data contained within the CRFs.

17.4 Quality Assurance, Audit and Inspection

This study may be subject to audit by the CRO, Sponsor or their representatives and Regulatory Authorities. These audits may be undertaken to check compliance with the requirements of GCP and can include:

- In-house study file audit
- Audit of computer database
- Audit of Clinical Study Report

- Audit of selected study sites, requiring access to subject medical records, study documentation and facilities, laboratories or pharmacies used for the study.

The study site, facilities and all data (including source data) and documentation will be made available for audit by the Investigator according to the ICH-GCP guidelines. The Investigator agrees to co-operate with the auditor during his/her visit and will be available to supply the auditor with CRFs or other files necessary to conduct that audit. Any findings will be strictly confidential.

In the event that a Regulatory Authority informs the Investigator that it intends to conduct an inspection, the Sponsor must be notified immediately.

17.5 Storage of Study Documents

The circumstances of completion or termination of the study notwithstanding, the Investigator has the responsibility to retain all study documents, including but not limited to the protocol, copies of CRFs, Investigator's Brochure, regulatory agency registration documents, ICFs, and EC correspondence.

The site will retain study documents for 15 years after completion of the study. This will include copies of the CRF. At the end of the 15-year period the site will contact the Sponsor who will determine any future arrangements for the storage of the study documents.

All CRFs and clinical trial data will be stored by the Sponsor or designee for a period of at least 15 years after termination of the study. The subject consent forms and re-identification lists will be archived with the Investigator for at least 15 years after termination of the study.

17.6 Registration and Publication of Study and Results

The trial will be registered by the Sponsor on a publicly accessible database e.g. <http://www.controlled-trials.com>.

The trial results will not be published without written consent by the Sponsor. Any oral or written communications /publications concerning the trial results will be reviewed and approved in writing by the Sponsor, which has a 60-day period to respond after receipt of the proposed communication/publication.

18. SCHEDULE OF ASSESSMENTS

Table I. Schedule of Assessments

	Screening Period	Treatment Period								Post-Study Medical	Safety Follow-Up
	Visit 1	Visit 2	Visit 3	Visit 4	Visit 5	Visit 6	Visit 7	Visit 8	Visit 9	Visit 10	Visit 11
Assessment	Day -28 to Day -1	Day 1	Day 2	Day 8	Day 15	Day 29	Day 30	Day 43	Day 57	Day 85	Day 210
Informed Consent	X										
Inclusion/Exclusion Criteria	X										
Demography	X										
Medical History	X										
Physical Examination ^d	X	X				X ^d				X	
Height, Weight, BMI	X										
Vital signs ^a	X	X ^b	X	X	X	X ^b	X	X		X	X
12-lead ECG	X										
Urinalysis	X			X				X		X	
Safety laboratory tests	X	X		X	X			X		X	X
HIV, Hep B and Hep C	X										
Pregnancy test ^c	X	X				X				X	
Alcohol urine test	X	X									
Drugs of abuse test	X	X									
Review of subject eligibility		X									
Randomisation		X									
Administration Investigational vaccine		X				X					
PD blood sample – antibody response		X			X	X		X	X	X	X
PD blood sample – PBMCs		X						X			
Assessment of injection site		X	X	X	X	X	X	X	X	X	
AE check						X				X	X
Con med check	X					X				X	X

Footnotes

- Heart rate, blood pressure, oral temperature and respiration rate.
- Vital signs at dosing Visit will be recorded pre-dose and at 2 and 4 hours post-dose.
- Serum pregnancy test at screening and post-study medical. Urine pregnancy test prior to each dose.
- Targeted medical examination (including assessment of the injection site(s) to determine eligibility for discharge at least 4 hours post-dose
- Photographs may be taken of injection site reactions as required.

APPENDIX I

INJECTION SITE TOLERABILITY ASSESSMENT

[figure not shown]
Tolerability assessments will be performed by a member of the clinical staff. An additional assessment by a physician will be made in the event of a local reaction being evaluated as moderate or severe. All measurements (in cm) refer to the longest dimension.

Redness

[figure not shown]
Grade	Description:
0 NONE	No visible redness
1 MILD	Greater than 0 to 2 cm (incl.) redness
2 MODERATE	Greater than 2 to 5 cm (incl.) redness
3 SEVERE	Greater than 5 cm redness

Bruising

Grade	Description:
0 NONE	No visible bruising
1 MILD	Greater than 0 to 2cm (incl.) bruising
2 MODERATE	Greater than 2 to 5cm (incl.) bruising
3 SEVERE	Greater than 5cm bruising

Induration

Grade	Description:
0 NONE	No swelling detected
1 MILD	Palpable "firmness" only
2 MODERATE	Less than or equal to 4 cm swelling
3 SEVERE	Greater than 4 cm swelling

Itching

Grade	Description:
N: ABSENT	
Y: PRESENT	

Pain

Subjects will be asked if they experience any pain. If the answer is yes, they will be asked to rate the level of pain on a scale of 1-10. Assessment of pain will commence after first injection.

Any other local reaction (for example: necrosis or ulceration)? Please specify

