Based on the results from clinical use of other protein vaccines adsorbed to Alhydrogel®, and other aluminium containing adjuvants transient local reactions at the injection site, including pain, oedema, bruising, erythema and induration, mainly of mild intensity, are likely to occur. In addition, flu-like symptoms, such as fatigue, malaise, myalgia, and mild to moderate headache may occur.

The protocol requires that subjects are monitored after vaccine administration (vital signs and general signs and symptoms), with regular follow-up visits for physician assessment and questioning regarding AEs will be conducted for all subjects in the study. All study subjects will be monitored for potential side effects of vaccination during the entire course of the study, as per the protocol, and adverse events must be appropriately followed up.

GBS-NN/NN2 vaccination is contraindicated in subjects known to suffer hypersensitivity reactions to vaccines or a known allergy to aluminium hydroxide. For the purpose of the study subjects who have experienced a significant illness in the four weeks prior to check in will be excluded. The vaccine should not be given to subjects with known or suspected immune deficiency, autoimmune diseases or who have an acute infection.

GBS-NN/NN2 should not currently be given to women known, or suspected to be, pregnant, or to nursing mothers. Currently GBS-NN/NN2 should only be administered to women of child-bearing potential if adequate contraceptive precautions are taken, accompanied by serum and/or urine pregnancy testing prior to vaccination and during follow up.

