12.2 Treatment Period and Post-Study Period

Subjects will be administered the primary dose of the appropriate dose of GBS-NN/NN2 or placebo according to the cohort and dosing schedule described in section 10.1 at Visit 2 and a second dose will be administered at Visit 6. All cohorts will incorporate sentinel dosing of 2 subjects in each cohort for the primary dose only: 1 on active treatment and 1 on placebo. No further subjects in that cohort will be dosed until 24 hours after dosing the second subject, provided that there are no serious or unexplained safety issues as determined by the Investigator.

The decision to proceed with administration of the primary dose in the subsequent cohort will be made as described in Section 12.5.

The following assessments will be carried out at these visits:

Visit 2

A general medical review, vital signs, urine pregnancy test, urine drugs of abuse test and alcohol urine test will be performed to re-confirm eligibility. Eligible subjects will then be randomised to receive the appropriate treatment as per the randomisation list for the cohort. A pharmacodynamic blood sample will be taken to measure pre-existing antibody levels and to obtain Peripheral Blood Mononuclear Cells (PBMCs) to assess cellular responses, prior to

dosing. Blood sample for haematology and serum biochemistry will be taken. Vital signs will be recorded at pre-dose (within 60 minutes of dosing), 2 (± 0.25) and 4 (± 0.25) hours post-dose. A general medical examination (including an assessment of the injection site) will be performed prior to discharge to ensure the subject is fit for discharge. At discharge subjects will be provided with oral temperature kit and instructed to record a temperature if they feel unwell in the seven days post dose.

Visit 3

Visit 3 will be performed 24 hours (± 2 hours) after administration of the primary dose and an assessment of the injection site will be performed, vital signs will be recorded and AEs and concomitant medications will be reviewed.

Visit 4

Visit 4 will be performed 1 week (± 1 day) after administration of the primary dose. An assessment of the injection site will be performed, vital signs will be recorded, safety blood samples for haematology and biochemistry will be collected, urinalysis will be performed and AEs and concomitant medications will be reviewed.

Visit 5

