Visit 5 will be performed 2 weeks (± 2 days) after administration of the primary dose. This visit will review of AEs and concomitant medications. An assessment of the injection site will be performed, vital signs will be recorded, safety blood samples for haematology and biochemistry will be collected and a pharmacodynamic blood sample will be taken to measure the antibody response.

Visit 6

Visit 6 will be performed 4 weeks (± 3 days) after Visit 2. An assessment of the injection site, AEs and concomitant medications review, urine pregnancy test, and a pharmacodynamic blood sample will be taken to measure the antibody response prior to administering the second dose. Vital signs will be recorded pre-dose and at 2 (± 0.25) and 4 (± 0.25) hours post-dose. A brief medical examination (including an assessment of the injection sites) will be performed prior to discharge to ensure the subject is fit for discharge. At discharge subjects will be provided with oral temperature kit and instructed to record a temperature if they feel unwell in the 7 days post dose.

Visit 7

Visit 7 will be performed 24 hours (± 2 hours) after administration of the booster dose and an assessment of the injection sites will be performed, vital signs will be recorded and AEs and concomitant medications will be reviewed.

Visit 8

Visit 8 will be performed 2 weeks (± 2 days) following Visit 6 and the following assessments will be performed: an assessment of the injection sites, vital signs will be recorded, safety blood samples for haematology and biochemistry will be collected, urinalysis will be performed, a pharmacodynamic blood sample will be taken to measure antibody response and to obtain PBMCs to assess cellular responses, and AEs and concomitant medications will be reviewed.

Visit 9

Visit 9 will be performed 8 weeks (± 2 days) following the first study vaccine administration and the following assessments will be performed: an assessment of the injection site and a pharmacodynamic blood sample will be taken to measure antibody response and AEs and concomitant medications will be reviewed.

Visit 10

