12.4 Time Windows for Visits

Vital signs will be performed within ±15 minutes of the scheduled time.

The time window for Visits 3 and 7 is ±2 hours.

The time window for Visits 4, 5, 6, 8, 9 and 10 is ± 2 days.

The time window for Visit 11 is ±2 weeks.

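### Appendix I sets no recall period for injection-site pain and no solicited record covers Days 2–8 or 30–43, so the by-visit reactogenicity table can understate how often pain occurred and how bad it was

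*Combined protocol and SAP*

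**What the plan says.** **The pain item.** Appendix I says: "Subjects will be asked if they experience any pain". For those who report some, the appendix adds a rating: "they will be asked to rate the level of pain on a scale of 1-10". It gives no look-back interval. Redness, bruising and induration have 0–3 severity grades; pain has only the number, with no mapping to mild, moderate or severe.

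**When the site is seen.** On each dosing day the site is checked before discharge, which the footnotes to Table 1 (section 18) put at 4 hours post-dose or later. Section 12.2 then gives, for dose 1, "Visit 3 will be performed 24 hours (± 2 hours) after administration of the primary dose" and "Visit 4 will be performed 1 week (± 1 day) after administration of the primary dose". For dose 2 it gives "Visit 7 will be performed 24 hours (± 2 hours) after administration of the booster dose" and "Visit 8 will be performed 2 weeks (± 2 days) following Visit 6". Section 12.4 states a different window for Visit 4: "The time window for Visits 4, 5, 6, 8, 9 and 10 is ± 2 days".

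**Between visits.** Under 12.2 the only home record in the week after a dose is a temperature, taken if the subject feels unwell. The diary card in 14.1 and 14.3 starts after Visit 10 (Day 85).

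**What is expected and reported.** Section 6.3 says that "transient local reactions at the injection site, including pain, oedema, bruising, erythema and induration, mainly of mild intensity, are likely to occur", and cites mild pain in roughly 30% of subjects given GBS-NN alone. In 15.4.2, local reactogenicity is the first item listed under the primary endpoint and is described by group and visit. Treatment-emergent adverse events, by relation and maximum intensity, sit under the same endpoint.

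**The concern.** A reaction that the protocol expects to be transient is measured by a question about the present, asked at widely spaced visits. If the form records current status, no later summary of the visit scores can recover an episode that came and went between two of them, or a peak that fell there. Pain already present at 24 hours is counted, but any later worsening is not rated.

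Two uses of the data are affected. The first is the local reactogenicity table within the primary endpoint. The second is the Cohort 2 decision in 12.5, which uses data through Visit 4 and lists injection-site assessments among the items reviewed. For dose 1 those scores come from the dosing day, 24 hours and Day 8. Intensity matters as well as frequency: section 6.3 treats pain worse than mild as unexpected.

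**Working it through.** The plan states no pain rate, power or precision target for this trial, so there is no figure of its own to reproduce. The check has two parts.

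**1. Length of the unscored gaps (12.2, 12.4, Table 1)**

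- Dose 1: Visit 3 (Day 2) to Visit 4 (Day 8): 8 − 2 = 6 days. With Visit 4 at ±1 day (12.2), 7 − 2 = 5 to 9 − 2 = 7 days. With ±2 days (12.4), 6 − 2 = 4 to 10 − 2 = 8 days. The two windows contradict each other and need to be reconciled.
- Dose 2: Visit 7 (Day 30) to Visit 8 (Day 43): 43 − 30 = 13 days. With ±2 days, 41 − 30 = 11 to 45 − 30 = 15 days.

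The ±2 hours at Visits 3 and 7 is ignored.

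**2. What a gap could do to the observed rate**

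Let p be the true risk of injection-site pain after a dose, m the share of painful episodes that start after the 24-hour visit and end before the next visit, and c the share of those that are captured as adverse events. Then:

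- rate shown by Appendix I = p(1 − m)
- rate if adverse-event reports are added = p(1 − m(1 − c))

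The documents give neither m nor c, so the values below are assumptions. I take p = 30%, borrowed from the GBS-NN figure in 6.3, and 24 vaccinated subjects per cohort: 24 × 0.30 = 7.2 expected with pain.

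| m | Appendix I alone | expected count of 24 | adding AEs, c = 0.5 | adding AEs, c = 0.9 |
|---|---|---|---|---|
| 0 | 30% | 7.2 | 30% | 30% |
| 0.10 | 27% | 6.5 | 28.5% | 29.7% |
| 0.25 | 22.5% | 5.4 | 26.25% | 29.25% |
| 0.50 | 15% | 3.6 | 22.5% | 28.5% |

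Example: m = 0.25 and c = 0.5 give 0.30 × (1 − 0.25 × 0.5) = 0.2625.

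If m is the same in both arms, the vaccine-minus-placebo difference shrinks by (1 − m) and the ratio does not change. With assumed risks of 30% and 10%, a 20-point difference becomes 20 × 0.75 = 15 points at m = 0.25, and the ratio stays at 3.

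The table covers frequency only. Loss of peak intensity cannot be put in numbers, because nothing in the documents describes how pain changes over time.

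**The case against.** The strongest reply is that between-visit pain has another route into the same primary endpoint. Under 14.3, subjects are told to report every adverse event spontaneously up to Day 85, and each report is entered in the eCRF. Adverse events are reviewed at Visits 4 and 8, the visits that close the two gaps. Each is graded under 14.2.1, and treatment-emergent events are tabulated in 15.4.2. The committee in 12.5 also sees adverse events.

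This stands, and it limits the point. A reader might infer that such pain is never scored and that the primary tolerability result is too favourable. The documents do not support that: they show a gap in one table of the primary endpoint and a possible direction of error. What the adverse-event route does not do is complete that table. It is unsolicited, uses a different scale, and no rule joins it to the 1–10 scores.

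Three further replies have force.

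- The appendix describes the question and may not be the form's exact wording; it does not forbid recall. That the item asks only about current pain is the natural reading, not a stated rule. The ambiguity is itself a reason to fix it, since staff could apply it differently.
- A reader might take the item as not tied to an injection site, or as allowing one score only after dose 2. The appendix title already makes it a site assessment, and 12.2 refers to sites in the plural at the Visit 6 discharge check and at Visits 7 and 8. What is missing is an instruction to label the scores by site.
- It is tempting to assume late onset and derive a large loss. Nothing in the documents supports late onset; section 6.3 speaks of reactions being transient, which concerns duration. The 30% may also be an observed rate from visit-based questioning, since the method of the earlier study is not described.

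**Conclusion.** The point holds in a limited form. Appendix I states no recall period, and no solicited symptom record covers the 6 days after Visit 3 or the 13 days after Visit 7. On the natural reading, pain that falls wholly between visits, or peaks there, is absent from the Appendix I scores and relies on unsolicited adverse-event reporting. The by-visit table in 15.4.2 can therefore understate the frequency and peak intensity of pain.

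The size is unknown. Under the assumed values it runs from nothing to a halving of the Appendix I rate (30% to 15%), and from nothing to 1.5 points (30% to 28.5%) if nine in ten missed episodes are captured as adverse events and counted. This rests on p = 30%, on the assumed m and c, and on reading the question as one about current pain. It should be fixed because the remedy costs little, not because a material bias has been shown.

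**What to change.** - **Appendix I, pain item.** At each existing visit after the first injection, record current injection-site pain (1–10) and worst injection-site pain since the last visit (1–10, with day of onset and day of end). Where both arms have been used, record separate scores labelled by dose.
- **Section 15.4.2.** Report the worst-since-last-visit score beside the current score, by group and visit. State how injection-site pain reported as an adverse event is combined with these scores, so that one episode is neither lost nor counted twice.
- **Sections 12.2 and 12.4.** Reconcile the two windows for Visit 4, since they set the length of the dose 1 recall interval.

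The cost is a few added questions on an existing form, asked by the same staff at the same visits, plus a column in the tables. The drawback is that recall over 6 to 13 days is less exact than a same-day score, which is why the current score is kept.
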